The most commonly used device for hemodynamic monitoring at Cottage is the Edwards FloTrac monitor, which requires arterial catheterization. Use of this device is our standard practice in treating patients with septic shock, with virtually all of our patients requiring the device both for continuous arterial pressure monitoring, as well as determination of cardiac output and stroke volume, and prediction of fluid responsiveness as described above. Unfortunately, it is well known that use of the FloTrac in septic patients is problematic, due to the state of their blood vessels from the disease state, as well as the effect of medications we use to treat their low blood pressure. We would like to test the accuracy of the FloTrac device in septic patients.

This study is designed to test the ability of the Flotrac device to predict the need for fluid administration in septic shock patients, requiring medications (vasopressors) to support their blood pressure. We will be using the measurements of cardiac output and stroke volume derived from the FloTrac, in conjunction with the passive leg raise test described above. Patients whose measurements suggest a need for more fluid with one or both devices, will receive a standard intravenous fluid bolus. Additionally, any patient who the treating clinician feels a fluid bolus is clinically indicated, regardless of the results of the PLR, will receive a fluid bolus. Clinicians may use ultrasound imaging of the inferior vena cava, or any other clinical information they routinely use, to make this determination. In this way false positives and false negatives will be apparent with both devices.

STUDY POPULATION

50 patients will be studied. Patients may have one or multiple assessments during their ICU stay as clinically indicated.

Inclusion Criteria:

- All adult patients with severe sepsis with hypotension, or septic shock, who have an arterial catheter with Flotrac monitor, with or without a central venous catheter, will be eligible for inclusion in the study.

Exclusion Criteria:

- Patient or legally authorized representative (LAR) decline consent.
- Pregnancy.
- Contraindication to raising legs or head to 45 degrees for 3 minute intervals.

Withdrawal and termination criteria:

- Patients may ask to withdraw from the study at any time.

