- Termination criteria would include removal or malfunctioning of arterial catheter or Flotrac device. Resolution of hypotension or shock state, and discharge or transfer from the ICU.

STUDY METHODS AND PROCEDURES

This will be a prospective, non-blinded, non-randomized study. Identification of appropriate patients meeting inclusion criteria, will be made by house staff and medical attending staff. Patients or their LAR will be asked to participate and sign consent, if in agreement.

When the clinical team feels assessment of intravascular volume status is appropriate, a passive leg raise maneuver (PLR) (see figure 1) will be performed, and clinical and hemodynamic variables (see data collection sheet- figure 2) will be recorded by the physicians and/or critical care nurse performing the maneuver. All patients will get a single fluid challenge after the initial PLR assessment, regardless of the result of the PLR. This fluid challenge can be cancelled by the treating physician based on clinical judgement. A physician may wish to cancel this fluid challenge if there is a risk of fluid overload with the patient. This fluid challenge will help us determine a false negative rate. After the first PLR, subsequent fluid challenges will only be given if the patient has greater than or equal to 10% increase in any of the 3 listed parameters, SVI, CI, or PP. PLRs will be done every 6 hours routinely (Figure 3), and additionally, if ordered by the physician. A physician can also order a fluid challenge at any time, based on clinical judgement regardless of PLR result. The fluid challenge will consist of intravenous administration of 500 ml of crystalloid solution (either saline or plasmalyte) given as rapidly as possible via a pressure bag, as is standard practice. If in the judgment of the treating physician, a smaller amount would be safer, the patient can be given a 250 ml bolus. Alternatively, the

patient may be given a bolus of either 250, or 500 ml of 5% albumin administered at the maximum IV infusion pump rate of 1200 ml/hr.

The type of fluid, volume, and duration of infusion of the fluid challenge will be recorded. Following the fluid challenge, the patient's hemodynamic response will be recorded, with the patient in the semi-upright 45 degree head up position.

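### After the first passive leg raise, test-negative patients get a fluid challenge only on physician order, and the ROC plan does not separate first from later assessments

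*Combined protocol and SAP*

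**What the plan says.** Study Methods and Procedures sets one rule for the first PLR and another for the rest.

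- **First PLR:** "All patients will get a single fluid challenge after the initial PLR assessment, regardless of the result of the PLR". The reason is stated: "This fluid challenge will help us determine a false negative rate". There is an exception: "This fluid challenge can be cancelled by the treating physician based on clinical judgement".
- **Later PLRs:** "After the first PLR, subsequent fluid challenges will only be given if the patient has greater than or equal to 10% increase" in at least one of SVI, CI and PP. The other route is clinical: "A physician can also order a fluid challenge at any time, based on clinical judgement regardless of PLR result".
- **Frequency:** "PLRs will be done every 6 hours routinely (Figure 3), and additionally, if ordered by the physician". Study Population sets 50 patients and adds: "Patients may have one or multiple assessments during their ICU stay as clinically indicated".
- **Dose safeguard:** "If in the judgment of the treating physician, a smaller amount would be safer, the patient can be given a 250 ml bolus".

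The Statistical Analysis section says that FloTrac's predictive value is the primary assessment and that its ability to assess responsiveness will be examined by ROC methods. It defines no analysis set, does not distinguish first from later PLRs, and does not mention assessments at which no challenge was given.

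Risks and Benefits acknowledges a remote risk of excess fluid. It then refers to challenges that the physician considers indicated and concludes that the study adds no risk. It does not mention the default first challenge.

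**The concern.** A PLR can be scored as right or wrong only if a fluid challenge follows and the response is measured. The investigators recognise this for the first PLR, which is why negatives are challenged by default there. At later PLRs the default disappears for negatives. False negatives and true negatives then go unobserved unless a physician orders fluid, while positives continue to be challenged. This is partial verification.

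Later PLRs can outnumber the 50 first ones, because they recur every six hours. An analyst who runs the ROC plan on every assessment with a measured response would mix a nearly complete sample with one depleted of test negatives. Sensitivity would look better than it is and specificity worse. The false-negative rate, which the first challenge was designed to reveal, would look too low if it is taken as one minus sensitivity.

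The risk text raises a separate, smaller matter. The first bolus goes ahead unless a physician stops it, and it is given partly for study purposes. The no-added-risk conclusion is argued from boluses that a physician chooses to give.

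**Working it through.** The plan gives no accuracy, prevalence, verification or precision figure, so there is nothing to reproduce. Only the rules and the 50 patients come from the protocol. Every rate below is an assumption chosen to show scale.

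**Set-up.** Assume 50% responders and true sensitivity = specificity = 80% at every PLR. Per 50 PLRs: TP = 20, FN = 5, FP = 5, TN = 20. Let *v* be the share of PLR-negatives that are challenged. With all positives challenged, and negatives challenged independently of true status:

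- apparent sensitivity = 20 / (20 + 5*v*)
- apparent specificity = 20*v* / (20*v* + 5)
- PPV = 20/25 = 80%; NPV = 20*v* / 25*v* = 80%

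**Pooling.** Take one fully verified first PLR plus *k* later PLRs per patient, with a fraction *r* of later negatives challenged. Then *v* = (1 + *kr*) / (1 + *k*). For ROC area, take responders as N(+0.842, 1), non-responders as N(−0.842, 1), the cut at 0, and values below the cut weighted by *v*.

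| *k* | *r* | *v* | Sensitivity | Specificity | ROC area |
|---|---|---|---|---|---|
| 0 | – | 1 | 20/25 = 80% | 20/25 = 80% | 0.883 |
| 1 | 0.5 | 0.75 | 20/23.75 = 84% | 15/20 = 75% | 0.881 |
| 3 | 0.3 | 0.475 | 20/22.375 = 89% | 9.5/14.5 = 66% | 0.87 |
| 3 | 0.1 | 0.325 | 20/21.625 = 92% | 6.5/11.5 = 57% | 0.860 |

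In the last row the apparent false-negative rate (one minus sensitivity) is 1.625/21.625 = 7.5%, against a true 20%. Under independent verification, sensitivity and specificity do not depend on the responder rate; the last row is the same at 40% and 60%.

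**Selective ordering.** Suppose physicians tend to pick likely responders at three later PLRs, with 20% of false negatives and 7.5% of true negatives challenged. That is (5 × 0.2 + 20 × 0.075)/25 = 10% of negatives overall. Pooled with the first PLR:

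- FN = 5 × (1 + 3 × 0.2)/4 = 2.0
- TN = 20 × (1 + 3 × 0.075)/4 = 6.125
- sensitivity = 20/22 = 91%
- specificity = 6.125/11.125 = 55%
- NPV = 6.125/8.125 = 75%, so NPV is now biased too

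**First PLRs only, with cancellations.**

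- 20% cancelled among PLR-negatives only (*v* = 0.8): 20/24 = 83%; 16/21 = 76%.
- 50% cancelled among PLR-negatives only (*v* = 0.5): 20/22.5 = 89%; 10/15 = 67%.
- 20% cancelled in both groups, unrelated to response: 16/20 = 80%; 16/20 = 80%.
- 20% cancelled in both groups, non-responders twice as often. Among positives, 20*c* + 5(2*c*) = 5, so *c* = 1/6, TP = 16.7 and FP = 3.3. Among negatives, 5*c* + 20(2*c*) = 5, so *c* = 1/9, FN = 4.4 and TN = 15.6. Sensitivity = 16.7/21.1 = 79%; specificity = 15.6/18.9 = 82%.

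Equal cancellation in the two PLR groups is therefore not enough to remove bias.

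**Precision with first PLRs only.** With 25 responders, 20/25 has a 95% Wilson interval of 61% to 91%. With 20 responders left after 20% cancellation, 16/20 gives 58% to 92%.

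**The case against.** The strongest reply is that the quantities the plan names barely move. Statistical Analysis speaks of predictive value and ROC. In the main scenarios PPV and NPV stay at 80%, and ROC area falls by at most 0.883 − 0.860 = 0.023. An approximate 95% interval for that area from 50 first PLRs (25 responders; Hanley–McNeil) is about 0.79 to 0.98, far wider than the shift. This stands for ROC area. For NPV it holds only if physicians order fluid in later negatives without regard to likely response, and the protocol says those orders rest on clinical judgement.

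Second, the false-negative rate is already tied to the default first challenge. That is fair as a statement of intent, but the analysis section does not carry it through. A reader might infer that the plan commits to pooling all PLRs. It does not say so; the defect is that nothing rules it out.

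Third, the size is illustrative. The number of later PLRs, the share of negatives challenged and constant accuracy over time are all assumed. The direction also needs later positives to be generally challenged. Because a rise in any of three parameters triggers a challenge, some patients negative on SVI alone will still be challenged, which softens the bias for a single-parameter ROC. All of this stands.

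Fourth, the data sheet (Figure 2) already records a trial number, the PLR measurements, and fluid type, amount and infusion time. First and later assessments can therefore be separated, and challenges not given can be identified. That makes the fix cheaper; it does not make it unnecessary.

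A reader might also infer that Objectives contradicts the first-challenge rule, because it describes only device-triggered and clinician-judged boluses. It does not say these are the only ones, so this is a drafting omission. Nor does Risks and Benefits deny the danger of excess fluid: it acknowledges it, and the safeguards appear in Study Methods and Procedures.

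**Conclusion.** The concern holds in conditional form. After the first PLR, observation of the outcome depends on the test result, and the ROC plan does not separate the two kinds of assessment. If later PLRs are pooled and later positives are generally challenged, a true 80%/80% at the 10% cut would be reported as something between 84%/75% and 92%/57% in the main scenarios. ROC area falls by no more than about 0.02. PPV and NPV are unbiased only when the challenged negatives are not selected on likely response. All rates are assumptions; the protocol supplies none.

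Two stronger conclusions are tempting and not supported. One is that the ROC analysis as a whole is invalidated: the damage falls on sensitivity, specificity and the false-negative rate at the cut, far more than on the area. The other is that first PLRs are free of bias. The default challenge largely protects them, but the result depends on how many challenges are cancelled, in which PLR group, and whether likely non-responders are cancelled more often (79%/82% and 89%/67% in the examples above).

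This is worth fixing before analysis, since the choice of set could change the reported specificity markedly. The risk wording is a fair but minor correction.

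**What to change.** 1. In Statistical Analysis, name first assessments as the primary set for ROC, sensitivity, specificity and the false-negative rate.
2. Treat later assessments as secondary: either descriptive, or adjusted for partial verification. A Begg–Greenes adjustment recovers 80%/80% when negatives are challenged independently of true status, but gives 76%/79% in the selective example, so it is not a full cure.
3. Report cancellations of the first challenge by PLR result, using the existing data sheet.
4. In Risks and Benefits, state that the first bolus is given by default and partly for study purposes, that it carries a fluid-overload risk, and that cancellation and the 250 ml option limit that risk. Adding the default challenge to the Objectives text would bring it into line.

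The cost is a text amendment and a tabulation of cancellations, with no extra patients or procedures. The downside is precision: later PLRs no longer add to the primary estimates, so an 80% sensitivity would rest on about 25 responders, with the 61% to 91% interval shown above.
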